7.2 Other Toxicities

- 7.2.1 Platelet Count Reductions
 - 7.2.1.1 If a **participant** develops a platelet count decrease of >25% from baseline with an absolute value remaining above 200,000/mm³, then dosing can continue.
 - 7.2.1.2 If the platelet count decreases from baseline by ≥ 25%, and the absolute value is between 150,000-200,000/mm³, then dosing of the study drug should be reduced to 10 mg QD. The CBC should then be repeated weekly until the platelet count either returns to > 200,000/mm³ or remains less than 10% below the value that led to the dose reduction for two consecutive values. If the platelet count returns > 200,000/mm³, and is > 1.10 times the value that led to the dose reduction, then BID study drug dosing can resume. The **participant** will then have weekly monitoring until the platelet count remains at a value that is greater than the value at BID dose resumption for at least two consecutive values. After resumption of the BID dosing if the platelet count decreases to < 200,000/mm³, then the dose will be decreased to 10 mg daily and remain at that dose except as noted in section 7.2.3.
 - 7.2.1.3 If the platelet count decreases by ≥ 25%, and an absolute value below 150,000/mm³, then the study drug should be discontinued. The CBC should then be repeated weekly until the platelet count returns to > 150,000/mm³.

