9.0 STATISTICAL CONSIDERATIONS

9.1 General Design Issues

A5336 is a randomized (2:1), prospective, open-label, 2-arm pilot clinical trial designed to assess the safety and tolerability of ruxolitinib, and to evaluate whether 5 weeks of treatment with ruxolitinib decreases IL-6 levels in HIV-1 infected **participants** virally suppressed on ART. **Participants** will be randomized 2:1 to receive ruxolitinib or no study treatment. **Participants** receiving ruxolitinib will be followed on treatment for 5 weeks, then for an additional 7 weeks off treatment, resulting in a total 12 weeks of follow-up; **participants** receiving no study treatment will be followed on-study for 12 weeks. The total sample size will be 60 **participants**.

- 9.2 Objectives
 - 9.2.1 Primary Outcome Measures
 - 9.2.1.1 Safety

Occurrence of any one of the following safety milestones (from entry to week 5).

- For **participants** with entry CD4+ T cell count < 700 cells/mm³, confirmed CD4+ decline > 33% of baseline and to < 350 cells/mm³.
- For **participants** with entry CD4+ T cell count ≥ 700 cells/mm³, a confirmed CD4+ T cell decline > 50 % of baseline.
- Confirmed HIV-1 RNA level **above the lower limit of quantification** in the absence of an interruption in ART.
- New or recurrent CDC category C AIDS-indicator condition.
- HIV-1 associated infection including Varicella zoster.
- Lymphoproliferative malignancies.
- Discontinuation of ruxolitinib due to thrombocytopenia.
- Grade 4 or recurrence of Grade 3 anemia/neutropenia.
- Any Grade 4 or recurrence of Grade 3 toxicity related to study drug.
- New diagnosis of pneumonia, sepsis, or bacteremia.
- 9.2.1.2 Tolerability
 - Occurrence of premature discontinuation of study treatment.
- 9.2.1.3 IL-6

Participant-specific change in the level of plasma IL-6 (using geometric means of two ELISA measurements at pre-entry and entry, and weeks 4 and 5).

- 9.2.2 Secondary Objective Measures
 - 9.2.2.1 Proportion of **participants** who experienced any one of the primary safety milestones during total follow-up (from entry to week 12).
 - 9.2.2.2 Summary of safety laboratories at baseline and weeks 1, 2, 4, 5, 10, and 12.
 - 9.2.2.3 Change in the level of plasma IL-6 from baseline to weeks 4, 5, 10, and 12.
 - 9.2.2.4 Changes in soluble markers of immune activation and inflammation in the peripheral blood (sCD14, TNF- α , IL-1 α , IL-1 β , mCSF, and neopterin) from baseline to weeks 4, 5, and 12.

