  - Confirmed HIV-1 RNA level above the lower limit of quantification in the absence of an interruption in ART.
  - New or recurrent CDC category C AIDS-indicator condition.
  - HIV-1 associated infection including Herpes zoster.
  - Lymphoproliferative malignancies.
  - Occurrence of Grade 2 or higher thrombocytopenia.
  - Grade 4 or recurrence of Grade 3 anemia/neutropenia.
  - Any Grade 4 or recurrence of Grade 3 toxicity.
  - New diagnosis of pneumonia, sepsis, or bacteremia.
- 4) Occurrence of protocol-defined reportable adverse events (all diagnoses, Grade 3 or higher sign/symptoms or laboratory values, any signs/symptoms or laboratory values that led to a change in treatment or met ICH, EAE, or SAE guidelines) at any post-entry time point.
- 5) Safety Laboratory values (estimated creatinine clearance, creatinine, AST (SGOT), ALT (SGPT), ANC, hemoglobin, platelet count) across all study weeks (at entry, week 1, and week 2, and arithmetic means at weeks 4 and 5, and at weeks 10 and 12).
- 6) Change in safety laboratory values (estimated creatinine clearance, creatinine, AST (SGOT), ALT (SGPT), ANC, hemoglobin, and platelet count) across all study weeks (at weeks 1 and 2, and arithmetic means at weeks 4 and 5 and at weeks 10 and 12).
- 7) Change in log10-transformed plasma IL-6 across all study weeks (geometric means of pre-entry and entry, and week 10 and 12).
- 8) Changes in soluble markers of immune activation and inflammation in the peripheral blood (sCD14, TNF- $\alpha$ , IL-1 $\alpha$ , IL-1 $\beta$ , IL-7, IL-10, IP-10, IL-18, mCSF, and neopterin) across study weeks from baseline (geometric mean of pre-entry and entry) to week 4/5 (geometric mean of week 4 and week 5) and week 12.

- 9) Changes in cellular markers of immune activation and inflammation in the peripheral blood (HLA-DR, CD25, CD38, CD69, CD127, Ki67, BCL2, a4b7, CX3CR1, PAR-1 measured on CD4 and CD8 cells; monocyte subsets (classical, inflammatory, and patrolling) defined by CD14 and CD16 expression; proportion of monocyte subsets (classical, inflammatory, and patrolling) expressing CCR2, CX3CR1, and CD163) from entry to weeks 5 and 12.
- 10) Level of plasma HIV-1 RNA at baseline and weeks 2, 5, and 12.
- 11) Change in CD4+ T cell counts from baseline (mean of pre-entry and entry) to weeks 2, 5, and 12.
- 12) Changes in HIV-1 reservoir (HIV-1 RNA by SCA, cellular HIV-1 total RNA and DNA) from entry to weeks 5 and 12.

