### 3 General Analysis Considerations

Study entry is defined as the date of the entry visit recorded on study initiation case report form.

The protocol-defined study week windows are modified for analysis purposes. For all analyses, the following window definitions will be used:

Pre-entry:	The last visit that occurred at least 24 hours prior to entry, but not more than 7 days before
Entry:	The visit after randomization, and prior to initiation of study treatment: Days [0-3]
Week 1:	The first visit in the window: Days [4, 22]
Week 2:	The second visit in the window: Days [4, 22]
Week 4:	The first visit in the window: Days [25, 39]
Week 5:	The second visit in the window: Days [25, 39]
Week 10:	The first visit in the window: Days [56, 93]
Week 12:	The second visit in the window: Days [56, 93]

Baseline values are the average of pre-entry and entry values, the week 4/5 values are the average of week 4 and week 5 values, and the week 10/12 values are the average of week 10

and 12 values; averages will be calculated using geometric means for log-transformed data and arithmetic mean for non-transformed data. If missing one of the pre-entry or entry values, then the available measure will be used as the baseline value, and similarly, if missing one of the week 4 or week 5 values or week 10 or week 12 values, then the available measure will be used as the week 4/5 value or week 10/12 value, respectively.

Analyses will be done among those in the as-treated population or among those in the safety analysis population (Cameron 2008), depending on the outcome; see the Statistical Methods section for details on populations for specific outcomes. The safety analysis population will consist of all participants randomized to the no-treatment arm and all participants who took at least one dose of ruxolitinib among those randomized to the ruxolitinib arm. The as-treated population is defined as participants who meet the following conditions: (1) have data at baseline and week 4/5, (2) for the ruxolitinib arm, remained on study treatment through week 4/5 and missed no more than 6 doses cumulatively, (3) did not change ART, use prohibited medications, or had confirmed virologic failure in this time period. Participants found to be ineligible after enrollment will be included in all safety analyses, but excluded from other analyses.

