### **4.2 Secondary Outcome Measures**

#### **4.2.1 Safety**

All summaries of secondary safety outcomes will be done in the safety analysis population.

In a similar manner to the primary safety analyses, tabular summaries will be provided for secondary outcomes (1-4), which will include frequencies and percentages overall and by study arm. Formal comparisons between study arms will contrast the proportion of participants who experienced any safety milestones on study from entry through week 12 as defined in secondary outcome (2) using a one-sided mid-p Fisher's exact test with 5% type-I error.

Levels and changes in safety laboratories (secondary outcomes 5 and 6) will be summarized with continuous descriptive summary statistics. Changes in safety labs will be formally compared at week 4/5 and week 10/12 via two-sided t-tests with 10% alpha and corresponding 90% confidence intervals.

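### Averaging the week 4 and week 5 safety laboratories can attenuate the on-treatment change for Arm A participants who stop, hold or reduce drug between those visits

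*SAP*

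**What the plan says.** Protocol 9.2.2.2 defines the outcome visit by visit: "Summary of safety laboratories at baseline and weeks 1, 2, 4, 5, 10, and 12".

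SAP 2.4.2 outcomes (5) and (6) cover creatinine clearance (CrCl), creatinine, AST, ALT, ANC, hemoglobin and platelets. Outcome (5) takes levels singly at entry and weeks 1 and 2, "and arithmetic means at weeks 4 and 5, and at weeks 10 and 12"; outcome (6) treats changes in the same way. SAP section 3 confirms that "the week 4/5 values are the average of week 4 and week 5 values", and uses the one available value if the other is missing.

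SAP 4.2.1 states: "Changes in safety labs will be formally compared at week 4/5 and week 10/12 via two-sided t-tests with 10% alpha". No test is planned at week 4 or week 5 alone.

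Four provisions determine which values enter the mean:
- The safety population includes "all participants who took at least one dose of ruxolitinib among those randomized to the ruxolitinib arm", so early stoppers stay in (SAP section 3).
- Participants who stop early remain on study, off treatment, to week 12 (Protocol 6.2.3).
- Week 5 is the second visit in days 25 to 39, whatever the drug status (SAP section 3).
- Laboratory results can themselves lead to a dose reduction, hold or stop (Protocol 7.2.1, 7.2.2, 7.2.3 and 7.2.8).

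The SAP's list of key updates (section 1.1) neither mentions nor explains the averaging. That list records changes to the SAP, so its silence shows only that no reason is given there.

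**The concern.** Averaging two visits suits a noisy efficacy marker. Protocol 9.4.1 gives that reason, lower variability and more power, in the IL-6 sample-size section; it speaks of markers and does not clearly extend to safety laboratories. A safety laboratory is different because the drug may be changed in response to the value. A low platelet count at week 4 can lead to less or no drug by week 5, and the recovering value is then averaged with the low one. This can happen only in Arm A, since Arm B has no study drug to change.

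At stake is the size of the on-treatment change in the only formal continuous comparison of these laboratories. Low platelets and anemia are the leading toxicities in the protocol's own background section. SAP section 1 says that all primary and secondary outcomes will be posted publicly, so the averaged version is the one that will be seen.

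**Working it through.** The plan states no figure for this point, so there is none to reproduce. The dilution is computed directly.

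**Inputs from the documents.** Arm A has 40 participants (SAP 2.1). Treatment is planned for 5 weeks, so both values are on drug, or at its end, for anyone who stays on it. Protocol 9.4.1 allows 20% for loss to follow-up and treatment discontinuation together: 0.20 × 40 = 8. All eight stopping between weeks 4 and 5 is therefore an extreme case.

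**Assumed inputs.** The documents do not give f, the share of Arm A stopping between the two visits, or r, the share of the fall recovered by week 5. Everyone is taken to be on drug at week 4.

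**One participant.** With an on-drug change D, week 4 shows D and week 5 shows D(1 − r), so the mean is D(1 − r/2). Full recovery (r = 1) leaves 50% of D; r = 0.5 leaves 75%. As an invented illustration, take platelets of 210,000 at entry, 140,000 at week 4 (a fall of 70/210 = 33%, below the 150,000 level in Protocol 7.2.1.3) and 210,000 at week 5. The week 4/5 value is (140,000 + 210,000)/2 = 175,000. The change is −35,000, against −70,000 at week 4.

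**Arm A mean, equal falls.** Week 4 = D; week 5 = D(1 − fr); week 4/5 mean = D(1 − fr/2). With r = 1:

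| Stop between visits | f | Week 4 | Week 5 | Week 4/5 mean |
|---|---|---|---|---|
| 0 of 40 | 0 | 100% | 100% | 100% |
| 1 of 40 | 0.025 | 100% | 97.5% | 98.75% |
| 2 of 40 | 0.05 | 100% | 95% | 97.5% |
| 4 of 40 | 0.10 | 100% | 90% | 95% |
| 8 of 40 | 0.20 | 100% | 80% | 90% |

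With r = 0.5, the last column becomes 99.4%, 98.75%, 97.5% and 95% for 1, 2, 4 and 8 stoppers.

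**Arm A mean, stoppers falling m times as far as the others, r = 1.** Week 4 = (1 − f) + fm; week 5 = 1 − f.
- 2 stoppers, m = 2: week 4 = 1.05, week 5 = 0.95, mean = 1.00; 1.00/1.05 = 95.2%.
- 2 stoppers, m = 3: 1.10, 0.95, 1.025; 1.025/1.10 = 93.2%.
- 8 stoppers, m = 2: 1.20, 0.80, 1.00; 1.00/1.20 = 83.3%.
- 8 stoppers, m = 3: 1.40, 0.80, 1.10; 1.10/1.40 = 78.6%.

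In these examples the separate week 5 mean is diluted twice as much as the average. What averaging removes is the undiluted week 4 value. If nobody changes drug between the visits, nothing is mixed.

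**The case against.** The strongest reply is that little is lost, because the SAP captures important falls elsewhere without averaging. Secondary outcome (4) counts Grade 3 or higher laboratory values and any value that changed treatment. Discontinuation for thrombocytopenia is a component of primary outcome (1). Grade 2 or higher thrombocytopenia, and Grade 4 or recurrent Grade 3 anemia or neutropenia, enter the between-arm composite and are tabulated singly. SAP 4.1.2 lists each early stop with its reason. Protocol 11.4.2 requires expedited reporting of platelets below 150,000/mm³ or a fall of 25% or more. This stands. A reader might infer that averaging hides a count such as 140,000, or masks toxicity; the documents do not support that.

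The mechanism is also narrow. A reader might infer a systematic shrinkage of the Arm A signal, but mixing needs a stop, hold or reduction between two particular visits. For someone off drug from before week 4, both values are off drug and by-week tables would show the same. Outside platelets, holds for anemia, neutropenia or AST/ALT begin at Grade 3, which is already a reportable event. Weeks 1 and 2 remain separate. All of this stands and limits the size.

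Averaging also buys precision. With within-participant correlation ρ, the SD of a two-visit mean is √((1 + ρ)/2) of the single-visit SD: 0.87 at ρ = 0.5 and 0.97 at ρ = 0.9 (assumed values). That is a reason to keep the mean as supplementary.

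The protocol planned only a summary here, so the t-test is a SAP addition. The Analysis Implementation Plan is redacted and may contain by-visit tables; their absence cannot be asserted. The defined outcomes and test would still be the averaged ones.

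The event outcomes do not fully replace a continuous comparison. A value that changed study drug has no counterpart in Arm B. Moderate falls that trigger no event are compared between arms only through the averages.

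**Conclusion.** The point holds as a minor one. The SAP replaces the separate week 4 and week 5 values listed in the protocol with their mean, tests only that mean on treatment, and has no rule separating on-drug from off-drug values. This can attenuate the on-treatment change in Arm A.

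The loss is up to half within one affected participant. It is about 1% to 10% of the arm mean if 1 to 8 of 40 stop between the visits with full recovery and equal falls, and about 21% in the extreme case of eight stoppers who each fall three times as far as the others. With no changes between the visits it is zero. All these rates are assumptions.

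The weakness is confined to the continuous comparison. It does not extend to the week 10/12 mean, where both visits fall after the planned treatment period and no on-drug and off-drug values are mixed.

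**What to change.** 1. Report weeks 4 and 5 separately, as Protocol 9.2.2.2 lists them. This restores the week 4 value, but by itself it does not make week 5 an on-drug value.
2. Add, by arm, each participant's worst value and worst change from entry: lowest platelets, hemoglobin, ANC and CrCl; highest creatinine, AST and ALT. Use scheduled visits from week 1 through week 5 only. After a platelet-related stop, Protocol 7.2.1.3 says "The CBC should then be repeated weekly until the platelet count returns to" above 150,000/mm³, and 7.2.1.2 also requires weekly counts after a dose reduction. These can add unscheduled counts in Arm A alone, and a minimum over more measurements would exaggerate its lowest value.
3. Flag values taken off drug or on a reduced dose.
4. Keep the week 4/5 mean as supplementary. The week 10/12 mean may stay as it is.

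The cost is a few tables and some further descriptive comparisons without multiplicity adjustment. Protocol 6.3.9 already has all seven laboratories recorded at every visit whatever their grade, so no new data, visits or participants are needed.

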#### 2.4.3 Other Outcome Measures

- 1) Changes in HIV-1 reservoir (2 long-terminal repeat sequences [LTRs], and integrated DNA) from entry to weeks 5 and 12.
- 2) Level of EBV, HSV, HHV-6, HHV-7, and HHV-8 shedding at pre-entry, entry, and weeks 1, 2, 4, 5, 10, and 12.

### 3 General Analysis Considerations

Study entry is defined as the date of the entry visit recorded on study initiation case report form.

The protocol-defined study week windows are modified for analysis purposes. For all analyses, the following window definitions will be used:

Pre-entry:	The last visit that occurred at least 24 hours prior to entry, but not more than 7 days before
Entry:	The visit after randomization, and prior to initiation of study treatment: Days [0-3]
Week 1:	The first visit in the window: Days [4, 22]
Week 2:	The second visit in the window: Days [4, 22]
Week 4:	The first visit in the window: Days [25, 39]
Week 5:	The second visit in the window: Days [25, 39]
Week 10:	The first visit in the window: Days [56, 93]
Week 12:	The second visit in the window: Days [56, 93]

Baseline values are the average of pre-entry and entry values, the week 4/5 values are the average of week 4 and week 5 values, and the week 10/12 values are the average of week 10

and 12 values; averages will be calculated using geometric means for log-transformed data and arithmetic mean for non-transformed data. If missing one of the pre-entry or entry values, then the available measure will be used as the baseline value, and similarly, if missing one of the week 4 or week 5 values or week 10 or week 12 values, then the available measure will be used as the week 4/5 value or week 10/12 value, respectively.

Analyses will be done among those in the as-treated population or among those in the safety analysis population (Cameron 2008), depending on the outcome; see the Statistical Methods section for details on populations for specific outcomes. The safety analysis population will consist of all participants randomized to the no-treatment arm and all participants who took at least one dose of ruxolitinib among those randomized to the ruxolitinib arm. The as-treated population is defined as participants who meet the following conditions: (1) have data at baseline and week 4/5, (2) for the ruxolitinib arm, remained on study treatment through week 4/5 and missed no more than 6 doses cumulatively, (3) did not change ART, use prohibited medications, or had confirmed virologic failure in this time period. Participants found to be ineligible after enrollment will be included in all safety analyses, but excluded from other analyses.

Confirmed virologic failure is defined as the occurrence of two sequential plasma HIV-1 RNA values above the lower limit of quantification in the absence of an interruption of ART; the confirmatory HIV-1 RNA should occur within 7 days of receipt of the results for the first test. In the event that a suspected virologic failure is not confirmed with a follow-up HIV-1 RNA test (i.e., there is no subsequent HIV-1 RNA available), this suspected virologic failure will be considered a *confirmed* virologic failure. Confirmed CD4 count decline is defined as two sequential CD4 counts meeting the respective criteria in the absence of an interruption in ART. Adverse events are classified as related (definitely, probably, possibly) or not related (probably not, not) by site investigators.

Biomarker data distributions will be assessed for normality, and any non-normal data will be log-transformed to the log-10 scale for analysis; it is anticipated that all soluble markers will be log-transformed. Descriptive summaries of continuous baseline characteristics will include frequency, frequency missing, mean, sd, median, IQR, 10th and 90th percentiles, and min/max; descriptive summaries of other continuous variables will use mean and sd, or median and IQR depending upon the corresponding analysis method. The frequency and percentage will be used for all categorical variables.

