6.0 CLINICAL AND LABORATORY EVALUATIONS

6.1 Schedule of Events

Evaluation	Screening Pro	Pre-Entry	Entry		(On-Study (W	Evaluati eeks)				
				1	2	4	5	10	12	Confirmation	Premature
Window	≤30 days before entry	≥24 hours after screening and ≤7 days before entry		± 3 days			± 7 days		of Virologic Failure	Treatment/Study Discontinuation Evals.	
Documentation of HIV-1	Х										
Medical History	Х		Х								
Medication History	Х		Х								
Complete Physical Examination		х									
Targeted Physical Examination	x		Х	х	Х	Х	х	х	х		Х
Clinical Assessments			Х	Х	Х	Х	Х	Х	Х		Х
Concomitant Medications	Х		Х	Х	Х	Х	Х	Х	Х		Х
Study Treatment Modifications	х		Х	х	Х	Х	х	Х	х		Х
ART Modifications	Х		Х	Х	Х	Х	Х	Х	Х		Х
Hematology	Х		Х	Х	Х	Х	Х	Х	Х		Х
Liver Function Tests	Х		Х	Х	Х	Х	Х	Х	Х		Х
Blood Chemistries	Х		Х	Х	Х	Х	Х	Х	Х		Х
Fasting Lipid Panel			Х				х				X (if prior to week 5)
Pregnancy Testing	Х		X1			If sus	spected				
Nadir CD4+ T cell Count			Х								
Documentation of Pre- ART CD4+ T cell Count			Х								
CD4+/CD8+	Х	X ²	Х		Х		Х		Х		Х

Evaluation	Screening Pre	Pre-Entry	Entry		(Dn-Study (Wo	Evaluati eeks)				
				1	2	4	5	10	12	Confirmation	Premature
Window	≤30 days before entry	≥24 hours after screening and ≤7 days before entry		± 3 days			± 7 days		of Virologic Failure	Treatment/Study Discontinuation Evals.	
Stored PBMCs for Other Immunologic Studies			Х				х		х		х
Stored Plasma Soluble Markers		Х	Х			Х	х		х		Х
Stored Plasma Soluble Marker:IL-6		Х	Х			Х	х	х	х		×
Documentation of Pre- ART HIV-1 RNA			Х								
Plasma HIV-1 RNA	Х		Х		Х		Х		Х	Х	Х
Stored Plasma HIV-1 RNA for Single Copy Assay			Х				х		х		Х
Stored PBMC Reservoir Assays			Х				х		х		Х
Stored Plasma/PBMC		Х	Х		Х		Х		Х		Х
Stored Oral Swabs for HHV		x	X	х	X	x	х	x	x		X
Plasma PK Collection for Arm A				х		х					X (if prior to week 4)
Medication Diary for Arm A (D=Distribute; C=Collect)			X (D)	X (C)	X (D)	X (C)					X (C) (if prior to week 4)
Adherence Assessment			Х	Х	Х	Х	Х	Х	Х		Х

¹Refer to section 6.2.2 for pregnancy testing at study entry. ²Only one CD4+/CD8+ is required if screening and pre-entry visits are combined.

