6.2.3 Post-Entry Evaluations

On-Treatment Evaluations

Evaluations must occur after randomization. Study visits must be scheduled on the weeks indicated in section 6.1, within the visit windows.

The weeks 1 through 5 study visits must be scheduled per section 6.1, the SOE table \pm 3 days.

Please note influenza vaccination is prohibited \leq 7 days prior to all study visits. The study visit will need to be rescheduled if the influenza vaccine was given \leq 7 days prior to a study visit. All other vaccinations are prohibited throughout the duration of the study.

Post-Treatment Evaluations

There will be 7 additional weeks of follow-up after 5 weeks of study treatment. **Participants** will undergo evaluations as outlined at weeks 10 and 12 in section 6.1. The week 10 and 12 study visits must be scheduled per the SOE ± 7days. Week 12 is the final study visit.

NOTE: **Participants** who discontinue treatment prematurely are followed on study/off treatment until study completion, i.e., week 12.

Virologic Failure

For **participants** who have suspected virologic failure, based on an HIV-1 RNA level above the lower limit of quantification, the site should query the **participant** about intercurrent vaccination, acute illness, or identified periods of nonadherance. If one of these conditions is suspected to account for the increased HIV-1 RNA, then no further evaluation is necessary until the next study visit. If none of these factors are present, a confirmatory HIV-1 RNA should be done within 7 days of receipt of the results of the first test. If the repeat HIV-1 RNA is **below the assay limit of quantification**, then no further evaluation is necessary. See section 7.5 for management of confirmed virologic failure.

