#### **4.2.2 Longitudinal Summaries of CD4 Count and plasma HIV-1 RNA**

Descriptive longitudinal summaries of levels and changes in CD4 cell counts and CD4 % will be provided by study arm and week. Formal comparisons between study arms of change from baseline will occur at all post-entry visits (week 2, 5, and 12); two-sided t-tests with 10% alpha will contrast differences between groups. In addition, change from week 5 (end of treatment) to week 12 (end of study) will also be examined. Participant narratives will be provided for those who had a protocol defined drop in CD4 cell counts (see primary safety endpoint).

Tabular summaries of categorized HIV-1 RNA levels (secondary outcome 10) by study week and arm will also be provided; no statistical inference will be done. HIV-1 RNA levels will be categorized as below or above the lower limit of quantification. Participant narratives will be provided for those who had any viral loads above the lower limit of quantification while on study.

All summaries will be done in the safety analysis and as-treated populations.

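### SAP visit windows separate paired visits only by order, so a missed week 1, 4 or 10 relabels the real week 2, 5 or 12 visit and drops its CD4 (and any reservoir) result from the planned comparisons

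*SAP*

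**What the plan says.** SAP section 3 replaces the protocol visit windows and sets the scope broadly: "For all analyses, the following window definitions will be used". Weeks 1 and 2 share days 4–22, weeks 4 and 5 share days 25–39, and weeks 10 and 12 share days 56–93. Within each pair the earlier week is the first visit in the window and the later week is the second; week 5 is "The second visit in the window: Days [25, 39". If one visit of a pair has no value, section 3 lets the other stand in, but only for the averaged week 4/5 or week 10/12 value. No averaged week 1/2 value exists, and the visible text has no rule for a window that holds a single visit.

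CD4 is not an averaged outcome after entry. SAP section 2.4.2, outcome 11, is "Change in CD4+ T cell counts from baseline (mean of pre-entry and entry) to weeks 2, 5, and 12". Section 4.2.2 adds that "Formal comparisons between study arms of change from baseline will occur at all post-entry visits (week 2, 5, and 12" and that "change from week 5 (end of treatment) to week 12 (end of study) will also be examined". In the protocol schedule (section 6.1), on-study CD4 is drawn only at weeks 2, 5 and 12, and the row "Stored PBMC Reservoir Assays" is marked after entry only at weeks 5 and 12. SAP section 4.2.4 tests total HIV-1 DNA at weeks 5 and 12. It limits the GEE and censored-normal models to participants with results at the time points of interest.

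**The concern.** Labelling by order works only when both visits of a pair take place. When the first is missed, the second becomes the first in its window. The CD4 result drawn at a genuine week 5 visit is then filed under week 4, where no CD4 is scheduled and no comparison is planned, and week 5 is empty for that participant. Weeks 1/2 and 10/12 behave in the same way.

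One missed visit does not take a participant off study: protocol section 8.2 requires two consecutive missed visits. So the right sample can exist at the right time and still leave a planned formal test. At stake are the CD4 comparisons at weeks 2, 5 and 12, the week 5 to week 12 change, and the reservoir comparisons if those assays are run (protocol sections 6.3.18 and 6.3.19 make them conditional).

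**Working it through.** The plan states no figure on this point, so there is none to reproduce. The check applies the printed rule to the protocol's own schedule and then sizes the loss.

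**Inputs**

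- Analysis windows: days 4–22, 25–39 and 56–93 (SAP section 3).
- Protocol windows: ±3 days for weeks 1 to 5; for the last two visits, "The week 10 and 12 study visits must be scheduled per the SOE" with ±7 days (protocol section 6.2.3). With target days 7, 14, 28, 35, 70 and 84 these are days 4–10, 11–17, 25–31, 32–38, 63–77 and 77–91.
- Randomised: 60, as 40 and 20 (protocol section 9.4.2).
- Assumption: a proportion p of 2–10% misses the first visit of a pair and attends the second, equally in both arms.

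**Step 1: apply the rule to every in-window day**

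| Pair | Second visit alone: mislabelled | First visit alone: correct | Both attended: correct |
|---|---|---|---|
| 1/2 | 7 of 7 days | 7 of 7 | 49 of 49 combinations |
| 4/5 | 7 of 7 days | 7 of 7 | 49 of 49 |
| 10/12 | 15 of 15 days | 15 of 15 | 224 of 224 |

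The count of 224 is 15 × 15 less the one combination with both visits on day 77. The rule is sound when both visits exist and always wrong for a lone second visit.

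**Step 2: see whether another rule restores the value**

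The stand-in rule fills only the averaged 4/5 and 10/12 values, whereas CD4 and reservoir outcomes are set at single weeks. Reading visit as a visit with that assay does not help. CD4 has one scheduled draw per window, so it would always count as first.

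**Step 3: loss at one week**

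Loss = 60p. With equal proportional loss in both arms, the standard error of the arm difference is multiplied by 1/√(1 − p).

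| p | Lost of 60 | Standard error factor |
|---|---|---|
| 2% | 1.2 (0.8 of 40, 0.4 of 20) | 1.010 |
| 5% | 3.0 (2 of 40, 1 of 20) | 1.026 |
| 10% | 6.0 (4 of 40, 2 of 20) | 1.054 |

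Reservoir analyses use the as-treated population. With the 48 evaluable participants that protocol section 9.4.1 anticipates, the loss is 0.96 to 4.8.

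**Step 4: loss for the week 5 to week 12 change**

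A participant is lost if either label is lost. Under independence the loss is 1 − (1 − p)²: 3.96%, 9.75% and 19% at p = 2%, 5% and 10%. That is 2.4 to 11.4 of 60 across the range, with standard error factors 1.020, 1.053 and 1.111. Without independence the loss lies between p (the same people miss both first visits) and 2p (different people): 2–4% at p = 2% and 10–20% at p = 10%.

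**Step 5: power**

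The plan gives no power for CD4 or reservoir outcomes, so the effect is set to give 80% power at full numbers (two-sided 10% t-test, 2:1 allocation, noncentral t). The results are the same for a total of 60 or 48.

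| Comparison | Loss | Power |
|---|---|---|
| One week, p = 2% | 2% | 79.3% |
| One week, p = 10% | 10% | 76.1% |
| Week 5 to 12, p = 2% | 3.96% | 78.5% |
| Week 5 to 12, p = 10% | 19% | 72.1% |

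**Not affected by a missed visit**

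Primary IL-6 uses the averaged values with the stand-in rule. The safety milestones run over intervals, and confirmed CD4 decline uses sequential counts. The by-week HIV-1 RNA tables would carry a wrong label, but for them "no statistical inference will be done", and narratives cover any value above the limit of quantification.

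**The case against.** The strongest reply is that the stand-in rule appears under general considerations with no restriction by outcome. Cellular markers are also defined at weeks 5 and 12, yet SAP section 4.2.3 averages weeks 4 and 5, and 10 and 12, as available. Read that way, a lone CD4 draw would serve as the week 4/5 or 10/12 value and nothing would be lost. This does not hold: the section 4.2.3 instruction covers outcomes 7 to 9 only, sections 4.2.2 and 4.2.4 name single weeks for CD4 and reservoir, and week 2 CD4 has no averaged value on any reading.

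Several other points stand as limits:

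- The analysis implementation plan is redacted and may hold a rule for one-visit windows. The finding concerns the visible rule.
- A CD4 result under week 4 or week 10 falls where none is scheduled, and section 4.2.2 describes week 5 as end of treatment and week 12 as end of study. An analyst could notice and override the label, but only by departing from the printed rule.
- The missed-visit rate and the 80% starting power are assumptions. Equal rates in the arms may not hold, since weeks 1 and 4 are pharmacokinetic visits for the ruxolitinib arm only.
- The day-by-day check covers in-window visits without extras. A late lone first visit (for example after day 10 in the first pair) is labelled correctly by the printed rule and wrongly by a nearest-day rule. An unscheduled visit can also upset date order: visits on days 7, 11 and 14 would make day 11 week 2. Both points tell against any rule based on dates alone, and so favour visit codes.

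**Conclusion.** The point holds, as a minor one. The printed rule gives a wrong label whenever the first visit of a pair is missed and the second is attended within its protocol window. That removes collected CD4 results from formal comparisons at weeks 2, 5 and 12, and reservoir results at weeks 5 and 12 if those assays are run.

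The loss is small: at the assumed 2–10% rate, about 1 to 4 percentage points of power at one week and about 2 to 8 points for the week 5 to week 12 change under independence. Only secondary outcomes are touched, and no bias between arms is claimed. Confidence in the labelling defect is high. The size depends wholly on a missed-visit rate that the documents do not give.

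**What to change.** In SAP section 3, assign each result to its scheduled visit code and keep the present windows as outer limits. Where no code exists, use date order if both visits of the pair are present, and state that unscheduled visits do not count in that order. If only one visit is present, use the nearest target day (7, 14, 28, 35, 70 or 84), and settle a tie at day 77 by which samples were drawn. For a lone second visit inside its protocol window, the nearest-day step is right on 7 of 7, 7 of 7 and 14 of 15 days for weeks 2, 5 and 12; the one exception is the day 77 tie.

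The cost is a few sentences and minor programming, with no new data. If the implementation plan already holds such a rule, it is enough to move it into section 3.
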